## 6 PLANNED ANALYSES

No statistical analysis plan (SAP) prepared in advance of the data can be absolutely definitive and the final Clinical Study Report (CSR) may contain additional tables or statistical tests if warranted by the data obtained. The justification for any such additional analyses will be fully documented in the final CSR.

### 6.1 Analysis Sets

Subjects excluded from the analysis sets and the reason for their exclusion will be listed in Appendix 16.2 of the CSR.

QMD Ref: Worldwide-TMP-ST-006-4.0 Effective: 12Aug2019	Governing QMD: Worldwide-SOP-ST-001
Confidentiality Statement	

This document is the property of Worldwide Clinical Trials Inc. and may not be duplicated, copied, altered or removed from company without prior approval from Worldwide Quality Assurance or in compliance with Worldwide Standard Operating Procedures.

Worldwide Clinical Trials Controlled Quality Management Document			
 WORLDWIDE CLINICAL TRIALS	Sponsor:	Cassava Sciences, Inc	
	Protocol Number:	PTI-125-05	
STATISTICAL ANALYSIS PLAN – PHASE 1			

### 6.1.1 Randomized Population

The Randomized Population is defined as all subjects who were randomized irrespective of receiving study drug.

### 6.1.2 Safety Analysis Set

The Safety Population is defined as all subjects who receive one dose of study medication.

### 6.1.3 Pharmacokinetic (PK) Population

The PK Population will include all evaluable subjects that complete all 4 periods of the study. Concentrations from subjects who drop out early will be analyzed and reported in the concentration-time listing only.

## 6.2 Derived Data

This section describes the derivations required for statistical analysis. Unless otherwise stated, variables derived in the source data will not be re-calculated.

### 6.2.1 Treatment Period / Visits

Each visit as per study schedule will be mapped to treatment period and analysis visit for summary tables as given below. Listings will reflect actual period and visit as defined in protocol.

Collected visit	Treatment Period	Analysis visit
Screening	-	Screening
DAY 0 Check-in	-	Check-in
DAY 1	Period 1	Day 1
DAY 2	Period 1	Day 2
DAY 3	Period 2	Day 3
DAY 4	Period 2	Day 4
DAY 5	Period 3	Day 5
DAY 6	Period 3	Day 6
DAY 7	Period 4	Day 7
DAY 8	Period 4	EOS / ET
Early Termination	Subject's last treatment period	EOS / ET

QMD Ref: Worldwide-TMP-ST-006-4.0 Effective: 12Aug2019	Governing QMD: Worldwide-SOP-ST-001
Confidentiality Statement	

This document is the property of Worldwide Clinical Trials Inc. and may not be duplicated, copied, altered or removed from company without prior approval from Worldwide Quality Assurance or in compliance with Worldwide Standard Operating Procedures.

Worldwide Clinical Trials Controlled Quality Management Document			
 WORLDWIDE CLINICAL TRIALS	Sponsor:	Cassava Sciences, Inc	
	Protocol Number:	PTI-125-05	
STATISTICAL ANALYSIS PLAN – PHASE 1			

## 6.2.2 Race

Where more than one race category has been selected for a subject, these race categories will be combined into a single category labeled “Multiple Race” in the summary tables. The listings will reflect the original selected categories.

## 6.2.3 Baseline

Baseline is defined as the last non-missing value (either scheduled, unscheduled or repeat) before the subject receives the first dose of study drug.

For variables that will be summarized by treatment, the baseline for each period is defined as the last non-missing value (either scheduled, unscheduled or repeat) that is collected before dosing of respective period.

## 6.2.4 Duration / Study Day / Time

Study day will be calculated as the number of days from first dose of *study drug*.

- date of event – date of first dose of study drug + 1, for events on or after first dose
- date of event – date of first dose of study drug, for events before first dose

## 6.2.5 Adverse Event

A treatment emergent adverse event (TEAE) is defined as an AE that emerges during treatment, having been absent pretreatment, or worsens relative to the pretreatment state. The following rules will be used to assign a TEAE to a treatment group:

- A TEAE will be assigned to the treatment received immediately before onset.
- Any TEAE reported within the washout period between doses will be attributed to the previous treatment.
- If a TEAE started in one treatment period and continued to subsequent periods, the event will be counted in period which AE started.

If a TEAE is missing relationship, it is assumed to be ‘probably related’ to the study drug for analysis purposes. Maximum severity will be assumed for an AE with missing severity. Adverse events that are reported as ‘possibly’ or ‘probably’ related will be considered as Related and events that are ‘unlikely’ related will be considered as Not Related.

QMD Ref: Worldwide-TMP-ST-006-4.0 Effective: 12Aug2019	Governing QMD: Worldwide-SOP-ST-001
Confidentiality Statement	

This document is the property of Worldwide Clinical Trials Inc. and may not be duplicated, copied, altered or removed from company without prior approval from Worldwide Quality Assurance or in compliance with Worldwide Standard Operating Procedures.

Worldwide Clinical Trials Controlled Quality Management Document			
 WORLDWIDE CLINICAL TRIALS	Sponsor:	Cassava Sciences, Inc	
	Protocol Number:	PTI-125-05	
STATISTICAL ANALYSIS PLAN – PHASE 1			

If a subject has multiple occurrences of same SOC and PT within a treatment period, then maximum severity and closest relationship will be separately flagged.

### 6.2.6 Conventions for Missing and Partial Dates

It is not expected that there will be any missing dates, however in the rare case that an Adverse Event (AE) start date or time is missing and it is unclear whether the AE is treatment emergent or not then a conservative approach will be taken and it will be assumed that the AE occurred after first dosing.

All dates presented in the individual subject listings will be as recorded on the Electronic Case Report Form (eCRF).

### 6.2.7 Inexact Values

In the case where a safety laboratory variable is recorded as “ $> x$ ”, “ $\geq x$ ”, “ $< x$ ” or “ $\leq x$ ”, a value of x will be taken for analysis purposes.

### 6.2.8 Not Done/Missing

For safety assessments where shift summaries are required, records will be imputed for all subjects who received IMP in the respective period in all scheduled visits and marked as ‘Not Done/Missing’ if either the subjects did not attend the visit, or discontinued or had missing assessment at the respective visit

### 6.2.9 Unscheduled Visits

Only scheduled post-baseline laboratory and vital signs values will be tabulated. Post-baseline repeat / unscheduled assessments will be disregarded, although these post-baseline assessments will be listed in the relevant appendices to the CSR.

### 6.2.10 PK Parameters

Concentration-time data for simufilam will be analyzed using noncompartmental methods in Phoenix™ WinNonlin® (Version 8.1 or higher, Certara, L.P.) in conjunction with the internet-accessible implementation of Pharsight® Knowledgebase Server™ (PKSO; Version 4.0.4, Certara, L.P.). Concentrations that are below the limit of quantification (BLQ) will be treated as zero in the data summarization and descriptive statistics.

QMD Ref: Worldwide-TMP-ST-006-4.0 Effective: 12Aug2019	Governing QMD: Worldwide-SOP-ST-001
Confidentiality Statement	

This document is the property of Worldwide Clinical Trials Inc. and may not be duplicated, copied, altered or removed from company without prior approval from Worldwide Quality Assurance or in compliance with Worldwide Standard Operating Procedures.

Worldwide Clinical Trials Controlled Quality Management Document			
 WORLDWIDE CLINICAL TRIALS	Sponsor:	Cassava Sciences, Inc	
	Protocol Number:	PTI-125-05	
STATISTICAL ANALYSIS PLAN – PHASE 1			

Blood samples for PK samples for the determination of simufilam will be collected at pre-dose (0), and at 0.333 (20 min), 0.667 (40 min), 1, 1.5, 2, 2.5, 3, 4, 6, 8, 10, 12, and 24 hours post-dose, for each treatment period.

Mean plasma concentration-time data will be presented graphically on both linear and semi-log scales using nominal time. Spaghetti plots and individual plots will be presented on both linear and semi-log scales using actual time. The following plots will be created:

- 1) Mean plot: Phase 3 Simufilam Tablet Fasted, Low-fat, and High-fat
- 2) Mean plot: Phase 2 Simufilam Tablet Fasted, Phase 3 Simufilam Fasted
- 3) All Subject plot: All subjects in one plot per Treatment
- 4) Individual Subject plot: Phase 3 Simufilam Tablet Fasted, Low-fat, and High-fat plotted together for each subject
- 5) Individual Subject plot: Phase 2 Simufilam Tablet Fasted, Phase 3 Simufilam Fasted plotted together for each subject

Individual plasma concentrations from subjects that were excluded from the PK Analysis Population will be listed in Concentration Listings.

Concentration-time data for simufilam in plasma will be analyzed using non-compartmental methods. The following descriptive statistics will be presented by treatment and nominal time: sample size (N), arithmetic mean, standard deviation (SD), coefficient of variation (CV%), minimum, median, and maximum.

In the PK analysis, BLQ concentrations will be treated as zero from time-zero up to the time at which the first quantifiable concentration is observed; embedded and terminal BLQ concentrations will be treated as “missing”. Actual time relative to dosing will be used in the PK analysis.

The following PK parameters will be calculated for simufilam for each treatment:

$C_{\max}$	Maximum plasma concentration determined directly from individual concentration-time data
$T_{\max}$	Time to reach maximum plasma concentration
$AUC_{\text{last}}$	Area under the plasma concentration versus time curve, from time 0 to the last quantifiable concentration ( $C_{\text{last}}$ ), as calculated by the linear trapezoidal rule

QMD Ref: Worldwide-TMP-ST-006-4.0 Effective: 12Aug2019	Governing QMD: Worldwide-SOP-ST-001
Confidentiality Statement	

This document is the property of Worldwide Clinical Trials Inc. and may not be duplicated, copied, altered or removed from company without prior approval from Worldwide Quality Assurance or in compliance with Worldwide Standard Operating Procedures.

Worldwide Clinical Trials Controlled Quality Management Document			
 WORLDWIDE CLINICAL TRIALS	Sponsor:	Cassava Sciences, Inc	
	Protocol Number:	PTI-125-05	
STATISTICAL ANALYSIS PLAN – PHASE 1			

C last	Last quantifiable concentration determined directly from individual concentration-time data
T last	Time of the last quantifiable concentration
AUC inf	AUC from the time of dosing extrapolated to infinity, calculated as: $AUC_{inf} = AUC_{last} + C_{last}/\lambda_z$
AUC Extrap	The percentage of AUC 0-inf obtained by extrapolation, calculated as: $AUC_{extrap} = [(AUC_{inf} - AUC_{last})/AUC_{0-inf}]*100$
$\lambda_z$	Apparent terminal elimination rate constant calculated by linear regression using the terminal log-linear phase of the logarithmic (log) transformed concentration vs. time data
T 1/2	The observed terminal elimination half-life, calculated as: $T_{1/2} = \ln(2)/\lambda_z$

### $\lambda_z$ Criteria

The following criteria will be used to report  $\lambda_z$ :

- At least three quantifiable concentrations will be used in the regression
- Cmax or data prior to Cmax will not be included in the regression.
- The adjusted regression coefficient (R^2 adj) should be  $\geq 0.80$ .

If these acceptance criteria are not met,  $\lambda_z$  and descriptive parameters ( $\lambda_z$  time range, Adj R^2, etc.) will be retained in a PK parameter table for informational purposes;  $\lambda_z$  will be flagged and excluded from summary statistics. Parameters calculated using  $\lambda_z$  (T1/2) will be reported as ND (not determinable).

If  $\lambda_z$  acceptance criteria are met and AUCinf is estimable, the following criteria are used to report AUCinf:

- The percentage of AUCinf based on extrapolation should be  $<30.0\%$ .

If the percentage of AUCinf based on extrapolation is 30.0% or greater, AUCinf and AUCextrap will be excluded from summary statistics, subsequent PK calculations and statistical analysis (e.g. ANOVA).

### 6.3 Conventions

All clinical data listings, summaries, figures and statistical analyses will be generated using SAS (Version 9.4 or higher).

QMD Ref: Worldwide-TMP-ST-006-4.0 Effective: 12Aug2019	Governing QMD: Worldwide-SOP-ST-001
Confidentiality Statement	

This document is the property of Worldwide Clinical Trials Inc. and may not be duplicated, copied, altered or removed from company without prior approval from Worldwide Quality Assurance or in compliance with Worldwide Standard Operating Procedures.

Worldwide Clinical Trials Controlled Quality Management Document			
 WORLDWIDE CLINICAL TRIALS	Sponsor:	Cassava Sciences, Inc	
	Protocol Number:	PTI-125-05	
STATISTICAL ANALYSIS PLAN – PHASE 1			

Summaries of the clinical data will be presented by treatment group / sequence or overall.

PK data listings, tables, figures, and statistical analyses will be generated using Phoenix® WinNonlin® (Version 8.1 or higher, Certara, L.P.) or SAS® (Version 9.4 or higher, SAS Institute Inc.). PK concentration-time data will be summarized by the number of non-missing observations (n), arithmetic mean (mean), standard deviation (SD), median, minimum (min), maximum (max), and coefficient of variation (CV%). PK parameter data will be summarized by n, mean, SD, median, min, max, CV%, geometric mean, and geometric CV%. Summary statistics that are not calculable due to lack of quantifiable data will be presented as NC in the descriptive statistic tables.

Treatment labels will be displayed as follows:

Fasted Simufilam	Low fat fed Simufilam	High fat fed Simufilam	Phase 2 Simufilam

Sequence group labels will be displayed as follows:

Sequence A	Sequence B	Sequence C	Sequence D

*Note: Footnotes will be added in all TLFs to clarify each sequence.*

Listings will be sorted in the following order subject, period, visit / date and parameter unless otherwise stated. All data will be listed, subjects who were not randomized will be displayed after the randomized treatment / sequence groups.

Safety parameters (continuous variables) will be summarized by the number of non-missing observations, mean, median, standard deviation, and minimum and maximum.

Categorical variables will be summarized by presenting the frequency and percent. Percentages will be based on the number of non-missing observations or the subject population unless otherwise specified. For each variable, all categories will be shown. Zero frequencies (but not the percent) within a category will be presented.

### 6.3.1 Decimal Places

Derived data, where it is known in advance that the result will be an integer, such as age, will be presented with zero decimal places.

Mean and median will be displayed to one more decimal place than the data, standard deviation will have two more decimal places, and the minimum and maximum will be displayed to the same

QMD Ref: Worldwide-TMP-ST-006-4.0 Effective: 12Aug2019	Governing QMD: Worldwide-SOP-ST-001
Confidentiality Statement	

This document is the property of Worldwide Clinical Trials Inc. and may not be duplicated, copied, altered or removed from company without prior approval from Worldwide Quality Assurance or in compliance with Worldwide Standard Operating Procedures.

Worldwide Clinical Trials Controlled Quality Management Document			
 WORLDWIDE CLINICAL TRIALS	Sponsor:	Cassava Sciences, Inc	
	Protocol Number:	PTI-125-05	
STATISTICAL ANALYSIS PLAN – PHASE 1			

number of decimal places as reported in the raw data. Percentages will be displayed with one decimal place.

For PK data, individual concentrations and PK parameters will be reported to 3 significant figures. Time (hour) will also be presented in 3 significant figures. For summary statistics, n will be reported as a whole number; mean, SD, median, min, max, CV%, geometric mean, and geometric mean CV% will be reported to the same precision as for individual data (3 significant figures). For ANOVA results, geometric means, least squares means, and the difference in least squares means will be reported to 3 significant figures. Percent ratios of the geometric least squares means and associated 90% confidence intervals will be reported to 2 decimal places. CV% (intra-subject variability) will be presented to 2 decimal places.

## 6.4 Subject Disposition

Subject disposition will be summarized as follows:

- The number of subjects included in Randomized Population; number and percentage of subjects included in the Safety and PK Populations will be summarized. Within the Safety Population, the number and percentage of subjects within each period and treatment will be summarized.
- The number and percentage of subjects who completed the study and who terminated early, along with subject's last period and treatment and reasons for early termination, will be summarized based on the Safety Population.

The Randomized Population will be based on planned treatment, and the Safety / PK Populations will be based on actual treatment received. Percentages for the Safety Population will be based on the Randomized Population; Percentages for all other categories will be based on Safety Population. Percentages for sub-categories will be based on main categories.

All subjects Disposition details, Treatment sequence and Population flags will be listed.

In Mock Shells: Table 14.1.1.1, Listing 16.2.1.1, Listing 16.2.3.1.

## 6.5 Protocol Deviations

A listing of protocol deviations will be provided.

In Mock Shells: Listing 16.2.2.1.

## 6.6 Demographic and Baseline Characteristics

QMD Ref: Worldwide-TMP-ST-006-4.0 Effective: 12Aug2019	Governing QMD: Worldwide-SOP-ST-001
Confidentiality Statement	
This document is the property of Worldwide Clinical Trials Inc. and may not be duplicated, copied, altered or removed from company without prior approval from Worldwide Quality Assurance or in compliance with Worldwide Standard Operating Procedures.	

Worldwide Clinical Trials Controlled Quality Management Document			
 WORLDWIDE CLINICAL TRIALS	Sponsor:	Cassava Sciences, Inc	
	Protocol Number:	PTI-125-05	
STATISTICAL ANALYSIS PLAN – PHASE 1			

Subject demographics will be summarized by Treatment sequence. Categorical and continuous variables will be provided in the same table. The following variables will be presented: age (years), sex, ethnicity, race, height (cm), weight (kg), BMI (kg/m^2). Percentages will be based on the respective population.

The summaries will be repeated for all Randomized, Safety, PK Populations (as per ICH E3 Guidelines). If the populations are the same, then demographic summary for Randomized Populations will be removed.

In Mock Shells: Table 14.1.2.1 to 14.1.2.3, Listing 16.2.4.1

## 6.7 Medical History

Previous and ongoing conditions at screening will be listed for the Safety Population. Conditions will be coded using the Medical Dictionary of Regulated Activities (MedDRA, version 24.0 or higher) and primary SOC and PT will be presented in listings.

In Mock Shells: Listing 16.2.4.2.

## 6.8 Prior and Concomitant Medications

Prior and concomitant medications will be listed for the Safety Population. Medications will be coded using the WHO Drug Dictionary (version Mar 2021 or later) and ATC levels will be presented in listings. Prior medications are defined as all medications that ended before the date of first dose of study drug. Concomitant medications are defined as medications ongoing on or after the date of first dose of study drug.

In Mock Shells: Listing 16.2.4.3.

## 6.9 Exposure to Study Drug

All dosing and meal consumption information will be listed for the Safety Population.

In Mock Shells: Listing 16.2.5.1.

## 6.10 Statistical Analysis of PK Data

Natural log transformed AUCinf (if data permit), AUClast, and Cmax, will be analyzed using a mixed effect model with sequence, period, and treatment as fixed effects and subject within sequence as a random effect. Estimates of the adjusted mean differences (Test-Reference) and corresponding 90% confidence intervals (CIs) will be obtained from the model. The adjusted

QMD Ref: Worldwide-TMP-ST-006-4.0 Effective: 12Aug2019	Governing QMD: Worldwide-SOP-ST-001
Confidentiality Statement	

This document is the property of Worldwide Clinical Trials Inc. and may not be duplicated, copied, altered or removed from company without prior approval from Worldwide Quality Assurance or in compliance with Worldwide Standard Operating Procedures.

Worldwide Clinical Trials Controlled Quality Management Document			
 WORLDWIDE CLINICAL TRIALS	Sponsor:	Cassava Sciences, Inc	
	Protocol Number:	PTI-125-05	
STATISTICAL ANALYSIS PLAN – PHASE 1			

mean differences and 90% CIs for the differences will be exponentiated to provide estimates of the ratio of adjusted geometric means (Test/Reference) and 90% CIs for the ratios.

For the food effect assessment, simufilam in the fasted state will be the intended reference treatment. The following comparisons will be made:

- High-fat (Test) vs. Fasted (Reference)
- Low-fat (Test) vs. Fasted. (Reference)
- Phase 2 tablet formulation (Test) vs. current tablet formulation (Reference; both Fasted).

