3. STUDY OBJECTIVES

The objectives of this study are 1) to assess the effect of food on the rate and extent of absorption of simufilam, and 2) to compare the pharmacokinetic profile of the Phase 3 formulation of simufilam to that of the earlier Phase 2 formulation. The new Phase 3 formulation has a higher percentage of active ingredient and is therefore smaller with a slightly different shape.

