4. SUMMARY OF STUDY DESIGN

This is a single-center, randomized, four-treatment, four-sequence crossover study in healthy volunteers to estimate the effect of food on the PK of simufilam following oral dosing of the Phase 3 simufilam 100 mg tablet. Additionally, the relative bioavailability of the Phase 3 tablet will be compared to the earlier Phase 2 simufilam 100 mg tablet, both in the fasted state. A total of twenty four (24) healthy volunteers (12 male and 12 female) will be enrolled into this study. Subjects will be randomly assigned to one of four treatment sequences (6 subjects/sequence) as shown in **Table 6**.

Table 6 Treatment Sequence

	Treatment Period 1			Treatment Period 2			Treatment Period 3				Treatment Period 4					
Sequence	Fasted	High	Low	Phase 2 Tablet	Fasted	High	Low	Phase 2 Tablet	Fasted	High	Low	Phase 2 Tablet	Fasted	High	Low	Phase 2 Tablet
Sequence A (n = 6)				X			X		X					X		
Sequence B (n = 6)	X							X		X					X	
Sequence C (n = 6)		X			X						X					X
Sequence D (n = 6)			X			X						X	X			

During each 48-h treatment period, subjects will be given a single oral dose of simufilam as displayed in **Table 6**. The administration of each dose of study drug will be separated by a 48-hour washout period. PK blood samples will be obtained prior to dosing and at specified intervals during the study (0-48 h post-dose for Treatment Periods 1 - 4). The observation period for safety will continue through the incarceration period.

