Natural log transformed AUC_{inf} (if data permit), AUC_{last}, and C_{max}, will be analyzed using a mixed effect model with sequence, period, and treatment as fixed effects and subject within sequence as a random effect. Estimates of the adjusted mean differences (Test-Reference) and corresponding 90% confidence intervals (CIs) will be obtained from the model. The adjusted mean differences and 90% CIs for the differences will be exponentiated to provide estimates of the ratio of adjusted geometric means (Test/Reference) and 90% CIs for the ratios.

For the food effect assessment, simufilam in the fasted state will be the intended reference treatment. The following comparisons will be made:

High-fat vs. Fasted

Low-fat vs. Fasted.

Phase 2 tablet formulation vs. current tablet formulation (both Fasted).

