14.4.2	Pharmacokinetic Parameters of Simufilam in Plasma after Administration of Phase 3 Simufilam 100 mg Tablet under Fasted Conditions, with a Low-fat Breakfast, with a High-fat Breakfast, and after Administration of Phase 2 Simufilam 100 mg Tablet under Fasted Conditions– PK Population	IP	-
14.4.3	Statistical Analysis of the Natural Log-Transformed Systemic Exposure Parameters of Simufilam Comparing Phase 3 Simufilam 100 mg Tablet Administered with a Low-fat Breakfast (Test) or a High-fat Breakfast (Test) to Phase 3 Simufilam 100 mg Tablet Administered under Fasted Conditions (Reference)– PK Population	IP	-
14.4.4	Statistical Analysis of the Natural Log-Transformed Systemic Exposure Parameters of Simufilam Comparing Phase 2 Simufilam 100 mg Tablet (Test) and Phase 3 Simufilam 100 mg Tablet (Reference)– PK Population	IP	-
14.6	Other Data		
	Not Applicable	-	-

QMD Ref: Worldwide-TMP-ST-006-4.0 Effective: 12Aug2019	Governing QMD: Worldwide-SOP-ST-001
Confidentiality Statement	

This document is the property of Worldwide Clinical Trials Inc. and may not be duplicated, copied, altered or removed from company without prior approval from Worldwide Quality Assurance or in compliance with Worldwide Standard Operating Procedures.

Worldwide Clinical Trials Controlled Quality Management Document			
 WORLDWIDE CLINICAL TRIALS	Sponsor:	Cassava Sciences, Inc	
	Protocol Number:	PTI-125-05	
STATISTICAL ANALYSIS PLAN – PHASE 1			

Figure Number	Figure Title	Validation Method
14.4.1	Mean Plasma Simufilam Concentration-Time Data after Administrations of Phase 3 Simufilam 100 mg Tablet under Fasted Conditions, with a Low-fat Breakfast, and with a High-fat Breakfast on Linear and Semi-logarithmic Scales– PK Population	IP
14.4.2	Mean Plasma Simufilam Concentration-Time Data after Administrations of Phase 2 Simufilam 100 mg Tablet and Phase 3 Simufilam 100 mg Tablet on Linear and Semi-logarithmic Scales– PK Population	IP
14.4.3	Plasma Simufilam Concentration-time Profiles for All Subjects after Administrations of Phase 3 Simufilam 100 mg Tablet under Fasted Conditions, with a Low-fat Breakfast, with a High-fat Breakfast, and after Administration of Phase 2 Simufilam 100 mg Tablet under Fasted Conditions on Linear and Semi-logarithmic Scales – PK Population	IP

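### Does naming the old Phase 2 tablet as Test and the new Phase 3 tablet as Reference spoil the formulation comparison?

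*SAP*

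**What the plan says.** Protocol section 3 gives the second objective as "to compare the pharmacokinetic profile of the Phase 3 formulation of simufilam to that of the earlier Phase 2 formulation"; SAP section 2 repeats it. The same protocol section identifies the newer product: "The new Phase 3 formulation has a higher percentage of active ingredient". Protocol section 4 adds that "the relative bioavailability of the Phase 3 tablet will be compared to the earlier Phase 2 simufilam 100 mg tablet", both given fasted.

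The analysis text has the opposite order. Protocol section 9.3 lists "Phase 2 tablet formulation vs. current tablet formulation (both Fasted") without Test or Reference labels. SAP section 6.10 adds the labels: "Phase 2 tablet formulation (Test) vs. current tablet formulation (Reference; both Fasted"). The title of Table 14.4.4 in SAP section 9 matches: "Comparing Phase 2 Simufilam 100 mg Tablet (Test) and Phase 3 Simufilam 100 mg Tablet (Reference"). SAP section 6.10 defines the output as the "ratio of adjusted geometric means (Test/Reference) and 90% CIs for the ratios".

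The only rule given for choosing a reference is confined to the meal comparisons: "For the food effect assessment, simufilam in the fasted state will be the intended reference treatment". SAP section 7 records no departure from the protocol analysis. On this point that is accurate, because the two analysis sections agree.

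**The concern.** In a formulation comparison, Test normally means the new product and Reference the established one. The objective and design summary read that way, but the analysis section and table title do not, and no reason is given. The fasted-reference rule cannot settle the matter, because both arms of this comparison are fasted.

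The worry is misreading. If the Phase 3 tablet delivered 85% of the Phase 2 exposure, Table 14.4.4 would print 117.65%. A reader who assumed that Test meant the new tablet would take a loss of exposure for a gain. Table 14.4.3 makes the slip easier, since the Phase 3 tablet (fed) is Test there and Reference (fasted) in the next table. No acceptance limits are stated, so the ratio and its interval are the main planned result for this objective. Their direction therefore deserves a check.

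**Working it through.** **The plan's own figure.** The direction of the comparison has no stated number behind it. The nearest is the sample size: 24 subjects for 80% power (Protocol 9.5, SAP 4). It cannot be reproduced, because neither document gives a within-subject CV, an expected ratio or limits. It can still be tested for dependence on direction (step 4).

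**1. Algebra.** Let d be the adjusted mean difference in log exposure, Phase 2 minus Phase 3, with standard error SE and t quantile t.

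- As planned: R = exp(d), with L = exp(d − t·SE) and U = exp(d + t·SE).
- With roles swapped, the contrast is −d with the same SE and t. The ratio is exp(−d) = 1/R and the interval is [1/U, 1/L].
- The log-scale width is 2·t·SE either way. The statistic changes only its sign, so the p-value is the same.

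**2. Illustrative ratios.** In percent, the inverted value is 10000/R.

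| Phase 3 / Phase 2 | Printed as Phase 2 / Phase 3 |
|---|---|
| 85% | 10000/85 = 117.65% |
| 90% | 10000/90 = 111.11% |
| 95% | 10000/95 = 105.26% |

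For an interval, 90.00% (82.00 to 98.50) inverts to 10000/90.00 = 111.11%, with limits 10000/98.50 = 101.52 and 10000/82.00 = 121.95. SAP section 6.3.1 prints ratios to two decimals, so a reader inverting the printed table loses almost nothing. A rounding error of 0.005 at 90.00 becomes about 0.005 × 10000/90² = 0.006 percentage points.

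**3. Simulation on the planned design.** 1000 trials were generated on the four sequences of SAP Table 1, with 6 subjects each. The assumptions were a true Phase 3/Phase 2 ratio of 1.1 and a log-scale within-subject SD of 0.25. Each trial was fitted with subject, period and treatment effects, once with each tablet as reference. Subject was fitted as a fixed effect; with complete balanced data this gives the same treatment contrasts as the planned random-subject model.

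- First trial, Phase 2/Phase 3: 0.9526 (0.8571 to 1.0588). Phase 3/Phase 2: 1.0497 (0.9444 to 1.1668). Check: 1/0.9526 = 1.0497, 1/1.0588 = 0.9444, 1/0.8571 = 1.1668.
- Over all trials, the two fits were reciprocal to within 4 × 10⁻¹⁵.
- Against assumed limits of 80.00 to 125.00%, 552 of 1000 passed, and the two directions disagreed in 0. This must be so, because 1/0.80 = 1.25.

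**4. Power.** Assumptions: the same limits, two one-sided 5% tests, s_w = √ln(1 + CV²), SE = s_w·√(2/24), and df = 3 × 24 − 6 = 66.

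| True ratio | Power at CV 20% | Power at CV 25% | Power at CV 30% | CV giving 80% power |
|---|---|---|---|---|
| 1.00 | 0.973 | 0.856 | 0.664 | 26.6% |
| 0.95 | 0.907 | 0.758 | 0.582 | 23.7% |
| 1/0.95 | 0.907 | 0.758 | 0.582 | 23.7% |
| 0.90 | 0.653 | 0.496 | 0.380 | 16.4% |
| 1/0.90 | 0.653 | 0.496 | 0.380 | 16.4% |

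Power is the same at a ratio and at its reciprocal. The 24 subjects serve either direction equally.

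**5. What the reader of the report will see.** The title of Table 14.4.4 states which tablet is Test and which is Reference. SAP section 6.3.1 has geometric means and least squares means reported with the model results. Table 14.4.2, under the summary rules of SAP section 6.3, gives geometric means of the PK parameters by treatment. Which tablet gives more exposure can be read directly, without knowing any convention.

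**The case for a change.** The strongest case for a change is that the objective and the analysis text point in opposite directions without a reason, that a relative bioavailability of the Phase 3 tablet reads most naturally as Phase 3 over Phase 2, and that aligning them would cost one line in each document and one table title. The wording mismatch stands. So does the remark that the Phase 3 tablet is Test in one table and Reference in the next.

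The rest carries less weight. The objective names two products but no numerator; only the analysis sections define a ratio, and they agree with each other and with the table title. A sensible reading is that the fasted Phase 3 tablet serves as the common reference arm for all three contrasts. The documents do not say so, but neither do they say that the food-effect rule was carried over by mistake. A need to bridge Phase 2 patient data to the new tablet is plausible but is not written as an objective, and an inverted ratio would serve it equally well. The contrast between 15% lower and 17.65% higher comes from the percentage scale; on the log scale used for analysis the two distances are equal.

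**Conclusion.** No change follows. The order of the two tablets differs between the objective and design text and the analysis text, but the planned ratio is the exact reciprocal of the one the objective suggests and is labelled correctly where it will be printed. The estimate, the precision on the log scale, the p-value and the power carry the same information either way, and no decision rule in either document depends on direction. The report's author can quote the ratio in whichever direction suits the text.

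This rests on two conditions. First, any limits applied later would be symmetric on the log scale, as 80.00 to 125.00% is; those limits are assumed here, since neither document gives any. Limits without that symmetry could make direction matter. Second, the Test and Reference labels in the title of Table 14.4.4 stay in the final output.
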